## 7.4 Description of Statistical Methods

### 7.4.1 General Approach

All data will be summarized using appropriate descriptive statistics, including mean, median, standard deviation, and range for continuous variables and frequency and proportions for categorical variables. Data will also be summarized graphically. Distributional assumptions will be assessed with suitable transformation conducted if indicated. Significance tests will use two-sided Type I error rate of 0.05.

### 7.4.2 Analysis of the Primary Efficacy Endpoint(s)

Detection of SARS-CoV-2 RNA by PCR will be the primary endpoint and will be compared between treatment groups (prophylaxis vs. no prophylaxis). Positive SARS-CoV-2 will be defined as a binomial variable (i.e., positive SARS-CoV-2 or no positive SARS-CoV-2) and analyzed using Wilcoxon rank analysis. Potential confounders of the primary endpoint will be addressed by using standard statistical matching techniques, such as propensity score matching, and logistical regression to assess for confounding by exposure risk, demographic factors and comorbidities that are known or suspected to affect the likelihood of developing SARS-CoV-2 infection.

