Statistical Analysis	All data will be summarized using appropriate descriptive statistics, including mean, median, standard deviation, and range for continuous variables and frequency and proportions for categorical variables. Data will also be summarized graphically. Distributional assumptions will be assessed with suitable transformation conducted if indicated. Significance tests will use two-sided Type I error rate of 0.05. The primary analysis will assess the number of HCW who test positive for SARS-CoV2 while on trial. Secondary endpoints include symptoms reported over time via web-based questionnaires, as well as other clinical endpoints such as quarantine, hospital admission, ICU admission, and mortality.
----------------------	--

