### 3 Objectives

Primary Objective	Primary Endpoint
To evaluate the efficacy of hydroxychloroquine (HCQ) for prophylaxis to prevent severe acute respiratory syndrome coronavirus 2 (SARS-CoV-2) infection among HCWs at high risk of occupational exposure to SARS-CoV-2 compared to eligible cohort that declines treatment	Frequency of infection with SARS-CoV-2 as determined by positive PCR for the virus on standard diagnostic tests.
Secondary Objectives	Secondary Endpoints
1. To characterize whether high-risk HCW who test positive for SARS-CoV-2 have an asymptomatic infection or report symptoms of COVID-19 in the 4 weeks preceding positive SARS-CoV-2	1. Symptom questionnaires performed once daily as currently mandated for HCW in high risk settings within UNMHS.
2. Determine role of occupational health exposure risk level on subsequent conversion frequency (mild-moderate-severe)	2. Online survey required once daily for all at risk HCW (existing document)
3. To assess the severity of any SARS-CoV-2 infection after prophylactic treatment with hydroxychloroquine.	3. Symptom questionnaires, Hospital admission rate, ICU admission rate, Mortality rate, PSI score of respiratory compromise
4. To assess the tolerability of hydroxychloroquine prophylaxis of SARS-CoV-2 in this population	4. Incidence of AEs or SAEs related to HCQ at study termination.
Exploratory Objectives	Exploratory Endpoints
1. To determine whether hydroxychloroquine reduces time lost from work	1. Days away from work
2. To assess the compliance of hydroxychloroquine prophylaxis	2. Frequency of missing dose
3. To assess whether HCQ benefits are different for specific AGPs or exposure on certain covid units (MICU v. ED v. covid rule out unit)	3. Frequency of positive test for SARS-CoV-2 related to AGP's or specific Covid-19 units.
4. To compare seroconversion between HCQ-treated and HCQ-untreated subjects on blood or plasma specimens.	4. Serological analyses at 4 times points (baseline, 30,60 and 90 days of study enrollment---with a 7-day window after each time point to complete analyses)

5. Metagenomic next generation sequencing of SARS-CoV-2 isolates detected in subjects	5. Sequence of viral isolates compared to published genomes and community-circulating SARS-CoV-2
---	--

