### **7.2 Statistical Hypotheses**

We will test the null hypothesis that the positive SARS-CoV-2 rate is the same among participants who opt to take HCQ as among participants who opt not to take HCQ. The alternative hypothesis is that the positive SARS-CoV-2 rate differs between the groups.

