### **7.3 Analysis Datasets**

The primary analysis data set will consist of positive SARS-CoV-2 outcomes for all enrolled participants. Sensitivity analyses will be conducted using the subset of HCQ participants who complete their entire course of treatment.

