### 7.4.3 Analysis of the Secondary Endpoint(s)

Secondary endpoints include symptoms reported over time via questionnaires, as well as other clinical endpoints such as hospital admission, ICU admission, and mortality. These binary clinical outcomes will be analyzed in a manner similar to that described above for the primary endpoint. Symptoms will be included as predictor variables. Antibody titers for SARS-CoV-2, measured as an exploratory endpoint in serum or plasma samples, will also be analyzed as binomial values. Positive values will be defined as a four-fold or greater increase in IgG antibody titers compared to baseline. Other descriptive analyses will be provided of the antibody titer results, including geometric mean, median, standard deviation, and titer range.

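### Section 7.4.2 pairs a crude Wilcoxon test with self-selected groups, does not say which of three analyses is primary, and leaves calendar period out of the adjustment list

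*Combined protocol and SAP*

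**What the plan says.** Groups are formed by choice. Section 5.2.2 puts those who decide to take HCQ in Group A and the rest in Group B, and section 7.2 tests whether "the positive SARS-CoV-2 rate is the same among participants who opt to take HCQ as among participants who opt not to take HCQ".

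Section 7.4.2 gives the analysis: "Positive SARS-CoV-2 will be defined as a binomial variable (i.e., positive SARS-CoV-2 or no positive SARS-CoV-2) and analyzed using Wilcoxon rank analysis". Its next sentence reads "Potential confounders of the primary endpoint will be addressed by using standard statistical matching techniques, such as propensity score matching, and logistical regression". Three kinds of factor are then listed: exposure risk, demographics and comorbidities. Calendar period, enrolment date and background incidence appear nowhere in section 7.

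No other place ranks the three methods. The Protocol Summary gives only the outcome: "The primary analysis will assess the number of HCW who test positive for SARS-CoV2 while on trial". Section 7.3 gives only the data set: "The primary analysis data set will consist of positive SARS-CoV-2 outcomes for all enrolled participants". Section 7.4.3 passes the same approach on to hospital admission, ICU admission and mortality: "These binary clinical outcomes will be analyzed in a manner similar to that described above for the primary endpoint".

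**The concern.** Without randomisation, the primary objective rests on the adjustment. The plan itself expects exposure to drive infection: it lists exposure risk as a confounder, and secondary objective 2 is to "Determine role of occupational health exposure risk level on subsequent conversion frequency". Crude and adjusted results can therefore differ, and the plan does not say which one counts. Matching also changes who is analysed, although section 7.3 keeps everyone enrolled.

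Calendar period is a second route to bias. The study lasts 12 months with up to 90 days per participant, so people can be at risk in different phases of the epidemic. Section 7.5 says uptake is unknown. Group B has its own ceiling of about 75, below all three control-group sizes tabulated in section 7.5 (175, 120, 90). If Group B fills first, late enrollees are all Group A.

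A crude primary result would mix who chose HCQ with what HCQ does. It could show an effect that is not there or hide one that is.

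**Working it through.** **1. The plan's own figures.** Section 7.5 gives detectable differences of 0.14, 0.15 and 0.17 for 175/175, 230/120 and 260/90. They reproduce as an unadjusted comparison of two proportions with continuity correction, HCQ rate 20%, two-sided 0.05:

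power = Φ{ [|pC − pT| − ½(1/nT + 1/nC)] / √[pC(1−pC)/nC + pT(1−pT)/nT] − 1.96 }

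Solving for 80% power gives 0.137, 0.149 and 0.166. For 35% against 20% at 230/120: (0.15 − 0.0063)/0.0509 − 1.96 = 0.86, so power is 80.6%. The figures are sound for a crude comparison and make no allowance for matching.

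**2. What Wilcoxon does here.** On a yes/no outcome its squared statistic is the Pearson chi-square times (N−1)/N. For 46/230 against 42/120: 9.427 × 349/350 = 9.400, with p = 0.00217 against 0.00214. The test is not invalid. It is a crude comparison that gives no effect estimate.

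**3. Confounding by exposure (assumed inputs).** Split 275/75. High exposure in 165/275 (60%) of Group A and 30/75 (40%) of Group B. Average risk is set for an equal mix of high and low exposure. With odds ratio 4 and average 35%, the risks are 50% (high) and 20% (low). A drug that does nothing then gives

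- Group A: 0.6 × 50% + 0.4 × 20% = 38%
- Group B: 0.4 × 50% + 0.6 × 20% = 32%

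That is a false harm of 6.0 points. At average 20% the risks are 30.2% and 9.8%, and the false harm is 4.1 points. In 100,000 simulated trials per row (differences are Group A minus Group B):

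| Exposure OR, average risk | True difference | Crude difference | Crude rejects | Exposure-stratified rejects |
|---|---|---|---|---|
| 4, 20% | 0 | +4.1 | 10% | 5% |
| 4, 35% | 0 | +6.0 | 14% | 5% |
| 2, 20% | 0 | +2.2 | 6% | 5% |
| 2, 35% | 0 | +3.1 | 7% | 5% |
| 4, 35%, relative risk 20/35 | −15.7 | −10.3 | 46% | 75% |
| 2, 35%, relative risk 20/35 | −15.4 | −12.6 | 61% | 74% |
| 4, 35%, relative risk 20/35, mix reversed | −14.3 | −19.7 | 94% | 80% |

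For example, in the fifth row the risk without drug over all enrolled is (195 × 50% + 155 × 20%)/350 = 36.7%, and 36.7% × 15/35 = 15.7 points. Setting the average risk to Group A's or Group B's mix instead moves the OR 4 no-effect results to 3.8 to 6.2 points and 9% to 15%.

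**4. If matching were primary.** One-to-one matching keeps at most 75 pairs and drops 275 − 75 = 200 of Group A. Exact crude power for 35% against 20% is 76.0% at 275/75 and 54.0% at 75/75, treating pairs as independent groups.

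**5. Calendar period (assumed inputs, no drug effect).** In the two-thirds case, Group B reaches 75 after 75/(120/350) ≈ 219 enrolments (144 A, 75 B); the other 131 are all Group A. Enrolment is even, follow-up is 90 days, and 90-day risk moves once from 35% to 20%.

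- Two-thirds row, 14 weeks: closure falls at 219/350 × 98 ≈ day 61. Group A looks better by 2.6 points (shift at day 61) to 3.9 points (day 98); crude rejection is 8% to 10%.
- Two-thirds row, 9 months: about 17% to 18% at worst.
- 260/90 row: 5% to 7%.
- 175/175 row: 8% to about 17% over 14 weeks, about 28% over 180 days and about 35% over 9 months, at worst.
- 275/75, no closure, uptake falling from 90% to 67%: 7% to 13% over 14 weeks, 10% to 25% over 9 months, for shifts of 35% to 20% or 10% to 35%.
- Logistic model with four enrolment blocks: about 4% to 6% throughout.
- Constant risk, or stable uptake with both groups filling together: no period bias.

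**The case against.** The plan does intend to adjust. It commits to matching and regression and names exposure first, so the bias in step 3 misleads only if the crude result stands as the answer. That Wilcoxon is primary is an inference from word order, and the test could also be read as applied to matched groups. This is fair, but it restates the gap: the text supports several readings and settles none.

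The sizes depend on chosen inputs. Narrowing the exposure mix to 55% against 45% brings crude rejection down to about 5% (OR 2) or 5.1% to 5.7% (OR 4). Eligibility aimed at high-exposure staff would tend to narrow the contrast. This stands: the figures show direction and plausible size, not what will happen.

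The calendar part is the least certain. The documents give no incidence by period, accrual pace, uptake trend or rule that Group A continues after Group B closes. The adjustment list might be read as open-ended, although the plan uses exposure risk level elsewhere for occupational exposure. What remains is that a 12-month epidemic study with unknown uptake has no stated protection against this bias.

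Finally, adjustment corrects only for measured factors. Where late periods contain no Group B, standardising over everyone extrapolates. Both points stand as limits of the remedy.

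**Conclusion.** The concern holds on all three counts: the test named is crude and the groups are self-selected; no primary result or effect measure is designated; and calendar period is absent from the adjustment list. With strong exposure imbalance (60% against 40%, OR 4), the crude test's false-positive rate is two to three times nominal, or its power for a real effect falls from about 75% to 46%. With OR 2 the false-positive rate is only 6% to 7%, and with balanced exposure there is no inflation. Period bias ranges from none to a rejection rate of about 35% in the most extreme case run. Exposure mix, odds ratios, risks and timing are assumptions; the gap in the text is not. It should be fixed before outcome data are examined. It does not make section 7.5 wrong, and Wilcoxon itself is not the error.

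**What to change.** In section 7.4.2 and the Protocol Summary, designate one covariate-adjusted comparison as primary. A suitable choice is a risk difference with 95% confidence interval, standardised over all enrolled participants from the logistic model already planned. Use the listed covariates, with exposure risk taken at baseline, plus calendar period of enrolment, and keep the list short for the number of events. Report the crude and any matched analysis as supportive. If Group B closes before Group A, add a sensitivity analysis restricted to periods when both were enrolling. In section 7.4.3, state that outcomes with too few events for the model are only described. Replacing Wilcoxon with chi-square is optional.

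The cost is mainly wording. The exposure survey is already scheduled at baseline, though its fields are not shown, and consents are dated. Section 7.5 need not change for this: simulated power of the logistic model with exposure and enrolment block at 275/75 is about 73% to 80% across the exposure scenarios tried, against 76% crude.

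There are drawbacks. Adding enrolment period raises the standard error of the log odds ratio by about 2% to 5% (260/90), 6% to 13% (two-thirds) or 17% to 31% (175/175) in the closure scenarios. The restricted analysis at 144/75 has 67% power. Some model dependence remains, and enrolment period is only a proxy for calendar time at risk. How participants who switch from Group B to Group A are classified is a separate decision that this change does not settle.

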## Schematic of Study Design

## 1 Background Information and Scientific Rationale

Severe acute respiratory syndrome coronavirus 2 (SARS-CoV-2) is a coronavirus novel to the human population discovered in December 2019; it is currently the cause of a global pandemic [1-3]. The World Health Organization (WHO) named the novel coronavirus severe acute respiratory syndrome coronavirus 2 (SARS-CoV-2) and the disease caused by SARS-CoV-2 coronavirus disease (COVID-19). As of 7 April 2020, person-to-person transmission has occurred worldwide, approaching 1.5 million cases and over 75,000 deaths. The WHO declared the COVID-19 pandemic a Public Health Emergency of International Concern on 30 January 2020 [4]. Most deaths and severe pneumonitis have occurred in the elderly or in persons with underlying pulmonary, cardiac, and other co-morbidities. SARS-CoV-2 infection can be asymptomatic, mild with self-limited pneumonia and other symptoms, or progress to life threatening respiratory involvement and multi-organ failure. The infection often appears less severe in children and younger adults [5]. Nevertheless, the burden to health and economic systems globally of this pandemic is already substantial and the pandemic has not peaked on a worldwide basis. No acquired immunity to this novel viral infection appears to exist in the human population globally and no effective treatment or preventative agent is licensed at this time.

An early report of 1700 cases of COVID-19 among health care workers (HCWs) caring for COVID-19 patients in China, included 5 deaths, in a published series of over 72,000 cases [6]. The number of HCWs infected with SARS-CoV-2 are increasing every day in USA and other countries.

On 3 March 2020, WHO declared a global shortage of personal protective equipment (PPE) leaving doctors, nurses and other frontline workers dangerously ill-equipped to care for COVID-19 patients [7]. By nature of their work caring for ill patients and evidence that SARS-CoV-2 can be transmitted from human-to-human, HCWs are at increased risk for COVID-19 infection. Many aerosol-generating procedures (AGP) are performed without knowing SARS-CoV-2 infection status. The SARS-CoV-2 epidemic has put tremendous strain on HCW

in all aspects. Scientists at the UNM HEALTH SYSTEMS are interested in studying the SARS-CoV-2 and strategies to protect HCWs in high-risk exposure settings.

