#### Total number of participants: 350 (Group A and B)

- Group A: up to 275 (HCW who choose to be provided HCQ)
- Group B: up to 75 (HCW who choose not to be provided HCQ)

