### 5.2 Study Schedule

#### 5.2.1 Schematic of Study Design

##### Schematic of Study Design

**Schedules of Activities for COVID-19 HCWP HCW HCQ Study**

Task	Screening/ Baseline	Daily (existing required survey)	30 Day (± 7days)	60 Day (± 7days)	90 Day (± 7days)	Early Termination or Clinically Suspected SARS- CoV-2
Consent	X					
Health history	X					
Exposure Survey (online)	X	X				X
Swab* for SARS-CoV-2 and plasma/serum sample	X		X	X	X	X
Hydroxychloroquine dosing initiation	X					
Adverse Events		X	X	X	X	X

\*Lab has confirmed ability to test samples from week over next weekend. Estimate up to 50 total per week (25 Sat, 25 Sun). Lab has also agreed to bank plasma and serum samples for delayed analysis.

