## **6 Assessment of Safety**

Participants will be asked about any potential side effects experienced during study period at the 30, 60, and 90 day visits. In addition, subjects will report any potential AE's as part of the modified, daily Employee Exposure Survey to be completed daily. All subjects are HCW's and a space will be included for them to enter any new symptoms they may have experienced. If none they will indicate none. In their busy, at-risk environment, enrolled HCW's will not be presented with a lengthy list of uncommon and rarely serious AE's reported with HCQ. Given concerns of cardiac toxicity (dysrhythmias) with the use of the study drug, particularly when combined with azithromycin, the following verbiage will be inserted into the informed consent form: "In addition, taking macrolide antibiotics (azithromycin, clarithromycin, erythromycin, spiramycin, telithromycin) while receiving hydroxychloroquine may increase the risk of serious heart rhythm problems (e.g. torsades de pointes). You may wish to consult with your physician before participating in the trial because you may be predisposed to these problems." The FDA warning about the use of hydroxychloroquine for treatment of COVID-19 (released April, 2020) will also be discussed in the consent form.

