## 7.5 Sample Size

The total sample size will be approximately 350 participants. We do not know in advance how many will opt to take or not take HCQ. The table below provides the detectable difference in positive SARS-CoV-2 rate for different proportions of participants in the treated and control groups. For example, if two-thirds of the sample opt to take HCQ, we will have 80% power to detect a difference in positive SARS-CoV-2 rate of approximately 15 percentage points (e.g., a 35% PCR positivity rate in the control group and a 20% PCR positivity rate in the HCQ group). These calculations assume a two-sided Type I error rate of 0.05. The exploratory endpoints remain independent of enrollment in Group A vs. Group B.

Treatment Group	Control Group	Detectable difference
175	175	0.14
230	120	0.15
260	90	0.17

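### The confounders named for the primary comparison omit calendar time, although self-selected, separately capped groups may enrol over months of a changing epidemic.

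*Combined protocol and SAP*

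**What the plan says.** Groups are formed by participant choice at enrolment (section 5.2.2). The ceiling for takers is "Group A: up to 275 (HCW who choose to be provided HCQ") and for decliners 75 (section 4.2.1); section 5.2.3 describes both ceilings as approximate. The Protocol Summary gives a 12-month study and up to 90 days per participant. No accrual period is stated. Section 1 says that "the pandemic has not peaked on a worldwide basis".

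For the primary endpoint, section 7.4.2 compares PCR positivity between groups with a Wilcoxon rank analysis. It then proposes matching on a propensity score, together with "logistical regression to assess for confounding by exposure risk, demographic factors and comorbidities that are known or suspected to affect the likelihood" (meaning the likelihood of infection). Section 7.3 takes all enrolled participants as the primary set, with no restriction to people enrolled concurrently. Its only sensitivity set is HCQ participants who complete treatment. Calendar time, enrolment date and community incidence appear nowhere in section 7.

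**The concern.** The risk of becoming PCR-positive in a 90-day window depends on when that window falls. In a randomised trial, concurrent allocation balances this. Here nothing does: choice of group can drift with time, and once one cap is reached only the other group recruits. If takers and decliners end up with different mixes of high-risk and low-risk periods, the comparison mixes the epidemic curve with the drug effect. The error can run either way: a false benefit, a false harm, or a real effect hidden. The covariates listed in section 7.4.2 describe the person and the job, so adjusting for them as written need not remove it.

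**Working it through.** **Inputs.** From the documents: caps of 275 and 75 (4.2.1, 5.2.3); 12 months and up to 90 days (Protocol Summary); laboratory capacity, "Estimate up to 50 total per week (25 Sat, 25 Sun") (footnote to the schedule in 5.2.1); group sizes and detectable differences (7.5); "Significance tests will use two-sided Type I error rate of 0.05" (7.4.1). Assumed, because the documents give no incidence over time: the risk in each phase and the share of each group enrolled in each phase.

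**1. The plan's own yardstick.** Section 7.5 says that with two-thirds taking HCQ "we will have 80% power to detect a difference in positive SARS-CoV-2 rate of approximately 15 percentage points", for example "a 35% PCR positivity rate in the control group and a 20% PCR positivity rate in the HCQ group". Starting from a 35% control rate, a normal-approximation calculation gives these detectable differences without / with continuity correction:
- 175 vs 175: 0.134 / 0.140 (plan 0.14)
- 230 vs 120: 0.140 / 0.145 (plan 0.15)
- 260 vs 90: 0.149 / 0.156 (plan 0.17)

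With the correction the first two rows agree to two decimals. The third does not; the plan's figure there is larger. Power for 35% vs 20% at 230 vs 120 comes to 85.7%, so the stated 80% is conservative. None of this affects the present point, and about 15 points serves as the scale for judging bias.

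**2. Room for enrolment to spread.** Twelve months less 90 days leaves up to about 9 months for enrolment. Four scheduled swabs each for 350 people is 350 x 4 = 1,400 swabs, and 1,400 / 50 = 28 weeks. Baseline swabs alone take 350 / 50 = 7 weeks. These figures make enrolment over several months plausible; they do not fix an accrual schedule.

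**3. Bias with no drug effect, two phases.** Group rate = (share in low phase x low risk) + (share in high phase x high risk). Assume risks of 10% and 30%.
- 70% of A and 30% of B in the low phase: A = 0.7 x 10% + 0.3 x 30% = 16%; B = 0.3 x 10% + 0.7 x 30% = 24%. Spurious difference 8 points in favour of HCQ.
- 60% and 40%: A = 0.6 x 10% + 0.4 x 30% = 18%; B = 0.4 x 10% + 0.6 x 30% = 22%. Spurious difference 4 points.
- 50% and 50%: both 20%. No bias.
- Equal risk in both phases: no bias at any split.

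Reversing the splits reverses the sign.

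In simulation at 230 vs 120, the crude two-proportion test (equivalent to a Wilcoxon test on a binary outcome) rejects the true null about 45% of the time in the first case and about 15% in the second. It stays at or just below 5% with equal splits. A Mantel-Haenszel test stratified by enrolment phase rejects about 5% of the time in each of these three cases.

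A smaller contrast, 20% and 35%, gives 3.0 points and 9% rejection when 40% of A and 60% of B are in the high-risk phase. With 30% and 70% it gives 6.0 points and 23%.

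**4. The caps alone.** Assume 75 B and 100 A enrol in a first phase, B then closes, and 175 A enrol in a second. With risks of 35% then 20% and no drug effect, A = (100 x 35% + 175 x 20%) / 275 = 70 / 275 = 25.5%, against 35.0% in B. That is a spurious 9.5-point benefit, with about 38% rejection. If risk rises from 20% to 35% instead, it is a spurious 9.5-point harm, with about 37% rejection. In this scenario 175 of the 275 takers have no concurrent control, and power for 35% vs 20% in the concurrent 100 vs 75 is about 60%.

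**The case against.** Several stronger readings are tempting, and the documents do not support them.

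- *That a shift in uptake is expected.* Section 6 says: "The FDA warning about the use of hydroxychloroquine for treatment of COVID-19 (released April, 2020) will also be discussed in the consent form". A reader might infer that this warning moves uptake over time. But it is consent-form text, and nothing shows that anyone enrols without it. If everyone reads the same form, any effect on uptake is uniform over time.
- *That swab capacity forces late starts.* The weekly figure is a laboratory estimate in a footnote, and participants who become PCR-positive leave the study (4.6), so not everyone will use four slots. A capacity limit also slows both groups alike: it lengthens enrolment without making it differ by group.
- *That the caps are hard.* Section 5.2.3 calls them approximate, and every control-group size in the 7.5 table (175, 120, 90) exceeds 75. The 15-point yardstick comes from a row with 120 controls, so the documents do not settle how large Group B will be or when it would close.
- *That risk at this site is known to be changing.* The epidemic statement in section 1 is worldwide; no local incidence is given for this single-site study.
- *That exposure risk means only a fixed occupational level.* Section 7.4.2 does not define it. The occupational wording comes from a secondary objective in section 3. If the covariate is built from the daily exposure survey (5.1.1), it would move with hospital caseload and absorb part of the time trend, though not community incidence.

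Self-selection by itself separates the groups by type of person, which propensity matching is meant to address. What stands is narrower. The named covariates do not include time, separate ceilings can leave one group recruiting alone, and nothing restricts or adjusts the comparison for that.

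**Conclusion.** The omission is real and worth correcting, but the bias is conditional. It needs both the taker/decliner mix and local infection risk to change during enrolment. If either stays constant, this source of bias is zero. Under the assumed two-phase inputs in which both change, the spurious difference runs from 3 to 9.5 points in either direction, against a design target of about 15. The phase risks and splits behind those figures are illustrations, not estimates. The reason to act now is that a time covariate chosen after outcomes are seen, in an open-label self-selected comparison, would carry little weight.

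Switching from Group B to Group A (5.2.3) is related but separate: a switcher's HCQ time always follows their untreated time, and section 7 does not say how switchers are classified. Adjusting for enrolment date does not resolve that.

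**What to change.** In section 7.4.2:

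1. Add enrolment date, as a smooth term or broad calendar periods, to both the propensity score and the logistic model.
2. State that the primary efficacy conclusion rests on that adjusted estimate. Otherwise the Wilcoxon comparison stays unadjusted whatever is added to the models.
3. Add a sensitivity analysis limited to periods when both groups were recruiting, and record the dates on which each group opens and closes.

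Exact matching within the same short period should not be required. With about 75 controls, and possibly an early close of Group B, it could discard many Group A participants.

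The cost is a few sentences. Enrolment dates must already exist, because the 30-, 60- and 90-day visits are timed from them. The adjusted estimate will be slightly less precise, and the sensitivity analysis will use a smaller sample if one group closes early, as the 60% power in the cap scenario shows. No study procedure changes.
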